1. Pregnant or lactating female (This is an FDA-required exclusion. In the future, if rTMS becomes a proven treatment for major depression, its safety in the context of pregnancy should be studied separately (Nahas et al. 1999).
2. Unable to be safely withdrawn, at least two-weeks prior to treatment commencement, from medications that substantially increase the risk of having

seizures. For the purpose of this study, those medications are listed in Appendix H (for example, theophylline).

3. Have a cardiac pacemaker.
4. Have an implanted device (deep brain stimulation) or metal in the brain.
5. Have a cochlear implant.
6. Have a mass lesion, cerebral infarct, increased intracranial pressure, or other active CNS disease, including a seizure disorder.
7. Known current psychosis as determined by DSM-IV or SCID (axis I, psychotic disorder, schizophrenia) or a history of a non-mood psychotic disorder.
8. Known current Bipolar I disorder as determined by SCID or a History of Bipolar I disorder.
9. Current amnestic disorders, dementia, BOMC > 10, delirium, or other cognitive disorders.
10. Current substance abuse (not including caffeine or nicotine) as determined by positive toxicology screen, or by history via SCID, within 3 months prior to screening.
11. Patients with an elevated risk of seizure due to TBI.
12. Participation in another concurrent clinical trial.
13. Patients with prior exposure to rTMS.
14. Active current suicidal intent or plan as evidenced by a score of 4 or 5 on the suicidal ideation portion of the CSSRS or the endorsement of an actual attempt, interrupted attempt, or an aborted attempt in the past 6 months. All patients will be required to establish a written safety plan involving their primary VA psychiatrist and the treatment team before entering the clinical trial (See Section X.B.8).
15. Unstable cardiac disease or recent (< 3 months previous) myocardial infarction.
16. Patient refuses to sign consent for participation in the study.

VI. METHODOLOGY

A. Recruitment

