The **North American National Adult Reading Test** (NAART; Blair & Spreen, 1989) will be used as an estimate of premorbid intellectual functioning. This measure consists of 61 items that are presented in two columns on a page for the participant to read. Participants are asked to read each word aloud as the examiner marks the errors on a score card.

All of the measures in the cognitive assessment are paper and pencil measures that will be administered by research staff. Staff will be trained in the proper administration and scoring of the cognitive assessment.

The cognitive assessment is expected to last approximately one hour at screening as well as at each follow-up.

23. Control Questionnaire. A questionnaire will be used before and after the first treatment session, and at the end of the final study visit to elicit patient perception of whether they were on active or sham rTMS treatment.

H. Adverse Events (AEs) and Adverse Device Effects (ADEs)

1. Adverse Device Effect (ADE) and Adverse Event (AE)

Definitions

An Adverse Device Effect (ADE) is defined by 21 CFR 812.3(s) and CSP Global Standard Operating Procedure (SOP) 3.6 as any adverse effect/event caused by or associated with the use of a device.

An Adverse Event (AE) is defined by the ICH for Clinical Safety Data Management and CSP Global SOP 3.6 as any untoward physical or psychological occurrence in a human subject participating in research. The AE does not necessarily have to have a causal relationship with the pharmacological product, study intervention or assessment. An AE can, therefore, be any unfavorable or unintended sign (including an abnormal laboratory finding), symptom or disease associated with the use of a medicinal (investigational) product.

Reporting

In CSP #556, collecting and recording all ADEs and AEs will begin at the time the patient signs the informed consent form and will continue throughout the follow-up phase. All events will be recorded on the appropriate case report form.

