Relatedness involves an assessment of the degree of causality between the study intervention and the event. Site investigators will be asked to provide an assessment of relatedness. The assessment provided by the site investigator is part of the information used by the sponsor to determine if the adverse event or effect presents a patient safety concern. Pursuant to CSP Global SOP 3.6, an ADE is deemed to be associated with the use of the study device if there is “a reasonable possibility that the experience may have been caused by the device or by participation in the trial.” Thus, all adverse events or effects with a reasonable causal relationship to the rTMS treatment should be considered “related”. A definite relationship does not need to be established. The following levels of relatedness will be used in CSP #556:

Not attributed to the rTMS treatment

Possibly attributed to the rTMS treatment

Attributed to the rTMS treatment

2. Serious Adverse Events (SAEs) and Unanticipated Adverse Device Effects (UADEs)

Definitions

Serious Adverse Events (SAEs) are a subset of adverse events and are defined by the ICH for Clinical Safety Data Management and CSP Global SOP 3.6 as any untoward medical occurrence that;

Results in death

Is life-threatening

Requires inpatient hospitalization or prolongation of existing hospitalization

Results in persistent or significant disability or incapacity

Is a congenital anomaly/birth defect or

Any other condition that, based upon medical judgment, may jeopardize the subject and require medical or surgical treatment to prevent one of the above outcomes

In addition, due to the potential increased risk of rTMS among depressed patients, seizures (not including syncope), suicide attempts, and any patient reports of significant hearing loss are considered Serious Adverse Events for the purpose of CSP #556 regardless of whether these events meet any of the above criteria. Participants will be assessed for subjective hearing problems during Screening, near midpoint of Acute Treatment Phase, End of Acute Treatment, and at the Final Follow-up Visit.

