An Unanticipated Adverse Device Effect (UADE) is defined by CSP Global SOP 3.6 as: "Any serious adverse effect on health or safety or any life-threatening problem or death caused by, or associated with, a device, if that effect, problem, or death was not previously identified in nature, severity, or degree of incidence in the investigational plan or application, or any other unanticipated serious problem associated with a device that relates to the rights, safety or welfare of patients". For this study an UADE is considered a category of SAE, which will be reported on the same form.

Collecting and Recording

For CSP #556, all SAEs and UADEs will be recorded on the SAE form, regardless of cause. The site investigator will be asked to determine whether the serious adverse event is related to:

rTMS Device

rTMS treatment

Disease progression of depression

Medications used to treat depression

Collecting and recording SAEs/UADEs will begin at the time the patient signs the informed consent form and will continue throughout the follow-up phase. For a patient who ends study participation prior to the study's completion date, unresolved SAEs will be monitored and

reported for 30 days after the “End of Study” date for that patient. In addition, the investigator must collect all SAEs reported to them for a period of 30 days after the study’s completion.

There are additional reporting requirements beyond using the CSP #556 policy and forms. Sites are responsible for submitting all information required by VA Central IRB policy. Please visit the VA CIRB website at <http://www.research.va.gov/vacentralirb/> for current policies, instructions and forms.

Specific VA Central IRB links

- a. What must be reported to the VA Central IRB:

<http://www.research.va.gov/vacentralirb/policies.cfm#4>

- b. Table of Reporting Requirements to the VA Central IRB:

<http://www.research.va.gov/programs/pride/cirb/CIRB-Table-of-Reporting-Requirements.pdf>

3. Expedited Reporting of Serious Adverse Events (SAEs) and Unanticipated Adverse Device Effects (UADEs)

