The CSP Clinical Research Pharmacy Coordinating Center (CSPCRPCC or PCC) will be responsible for initially evaluating all serious adverse events for patient safety concerns and will confer with the Study Chair (or another physician member of the Executive Committee if the Study Chair is unavailable) as required during this evaluation process. After being reviewed by the Study Chair, the PCC Director and the CSPCC Director, any event deemed to be related, serious and unexpected will be reported to CRADO, study investigators, and FDA.

Expedited Reporting by sites to the Study Sponsor (CSP): All Serious Adverse Events (SAEs) which includes Unanticipated Adverse Device Effects (UADEs) require prompt reporting, within 72 hours of the site investigator being made aware of the event. The SAE reports will be forwarded within 72 hours of discovery of an SAE by the study site to Perry Point CSPCC who will immediately notify the CSPCRPCC and the Chairman’s Office. If the SAE is not resolved at the time the event is reported, the site must monitor and provide SAE follow-up information at least every 30 days until the SAE becomes resolved. The site must handle requests for SAE Follow-up information in the same prompt manner that the original SAE reports are handled

Expedited Reporting by the Sponsor to the FDA: The Chairman and Study Pharmacist will review the SAE report to assess completeness of documentation and to determine whether the SAE requires expedited reporting to the FDA.

Specifically, if an event meets the criteria for unexpectedness (i.e., not previously reported), seriousness (by definitions in section H.2.), and relatedness, it will be reported to the FDA within 10 working days for UADEs and within 7 calendar days for unexpected SAEs (Safety Reports) of the sponsor (Cooperative Studies Program) receiving the report as required by regulation.

4. Data Monitoring Committee (DMC) Reporting of Adverse Events, Adverse Device Effects, Serious Adverse Events, and Unanticipated Adverse Device Effects. The Clinical Research Pharmacist and the Study Biostatistician will generate tabulations of AEs and SAEs and present a summary of these to the DMC on a schedule set by the DMC. The DMC will also determine when they should be unblinded to treatment assignment for the reviewing of adverse event data. The DMC will advise the CSP Director concerning whether the study should continue or be stopped for safety reasons.

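### The quoted relatedness standard includes trial participation, but the AE relatedness levels and the SAE cause list leave no place for it

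*Protocol*

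**What the plan says.** Section VI.H.1 opens its account of relatedness with the study intervention: "Relatedness involves an assessment of the degree of causality between the study intervention and the event". It then cites the SOP, under which an adverse device effect is associated with the device if there is "a reasonable possibility that the experience may have been caused by the device or by participation in the trial". The sentence that follows is introduced as a consequence of this and says that "all adverse events or effects with a reasonable causal relationship to the rTMS treatment should be considered" related. Three levels are then fixed for the study: not attributed, possibly attributed and attributed. Each is worded against the treatment, as in "Possibly attributed to the rTMS treatment".

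For SAEs, section VI.H.2 asks the site investigator about four causes: the rTMS device, the rTMS treatment, "Disease progression of depression", and medications used to treat depression.

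On timing, section VI.H.1 states that "collecting and recording all ADEs and AEs will begin at the time the patient signs the informed consent form". The same start applies to SAEs in VI.H.2.

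Section VI.H.3 makes relatedness one of three conditions for expedited reporting to the FDA: "if an event meets the criteria for unexpectedness (i.e., not previously reported), seriousness (by definitions in section H.2.), and relatedness". The same section applies the same three conditions to reports to the Chief Research and Development Officer and to study investigators.

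Two eligibility criteria attach medication conditions to taking part. Section V.B, item 2 excludes a patient who is "Unable to be safely withdrawn, at least two-weeks prior to treatment commencement, from medications that substantially increase the risk" of seizures. Section V.A, item 8 requires that a patient on psychotropic medication be willing to keep that regimen stable through the acute phase.

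**The concern.** The premise and the rule drawn from it do not match. The premise covers two sources of harm, the device and participation in the trial. The rule keeps one. Both recording schemes follow the rule, so the site is never asked about participation.

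This matters because the trial creates exposures that are not stimulation. A patient taken off a drug in order to enter, or kept on an unchanged regimen in order to stay, may be harmed by that condition. Under the quoted standard such an event is associated. Under the working definition it is not. Relatedness is a condition for onward and FDA reporting, so the classification has a consequence: an event can meet the standard that the protocol quotes and still not be passed on as related.

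**Working it through.** No arithmetic applies. The check sets the provisions side by side and runs example events through them.

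**What each provision covers**

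| Provision (Protocol) | rTMS device or treatment | Trial participation or study procedure | Other |
|---|---|---|---|
| SOP standard, VI.H.1 | yes (device) | yes | – |
| Definition of related, VI.H.1 | yes (treatment) | no | – |
| AE levels, VI.H.1 | 3 of 3 refer to treatment | 0 of 3 | – |
| SAE causes, VI.H.2 | 2 of 4 | 0 of 4 | 2 of 4 (disease progression; depression medications) |

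**Example events**

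1. *Non-serious event caused by withdrawal of a seizure-risk drug, before the first session.* Withdrawal must come at least two weeks before treatment, and screening after consent lasts two to four weeks (section VI.B), so withdrawal can fall inside the collection window. The event meets the participation limb of the standard. On the AE scale the only accurate level is 'not attributed'.

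2. *Serious event caused by the same withdrawal.* Section V.B, item 2 gives theophylline as an example. An SAE from stopping it is not due to the device, the treatment, progression of depression or a depression medication, so none of the four listed causes fits.

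3. *Serious event attributed to holding the regimen stable.* This can be entered under disease progression or depression medications. Neither entry shows that a trial condition contributed.

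4. *Event caused by motor threshold testing at the end of screening* (section V.A, item 6). The SAE list can take it under the device. The AE levels name only the treatment, so it is unclear whether they cover it.

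**Consequence.** The only definition of related in the text at hand is the one in VI.H.1, and VI.H.3 supplies no broader one. Events of types 1 to 3 satisfy the quoted standard but not that definition. If serious and unexpected, types 2 and 3 can then fail the relatedness condition in VI.H.3.

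**The case against.** The strongest reply is about scope. The SOP clause says when an adverse device effect counts as associated with the device; it is not written as a rule for all adverse events. The protocol's opening sentence on relatedness speaks of the study intervention, and the three levels agree with it. This has weight, but the protocol itself carries the clause over to all adverse events or effects in the next sentence. If a device-only rule was meant, the passage is still inconsistent and needs reconciling.

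The second reply is that the site's code does not decide reporting. That stands. Section VI.H.1 treats the site's assessment as one input to the sponsor's decision, and VI.H.3 has senior study officials review events. But the site is never asked about participation, so the input is incomplete.

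Several stronger readings are tempting and are not supported:

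- *That the SAE list offers only the device or the treatment.* It has two further causes. What it lacks is a category that marks an event as trial-caused.
- *That no screening event can be coded as related, so all screening time is affected.* Motor threshold testing uses the device before randomization, and a resulting SAE can be coded to the device. Withdrawal concerns only patients on the listed drugs. Section X.B.8 says that being on such drugs would likely have led to exclusion. Total screening time therefore does not measure this exposure.
- *That serious events go unseen.* Section VI.H.2 records all SAEs whatever the cause, and VI.H.3 sends them to the sponsor within 72 hours. Suicide attempts (X.B.8) and seizures (X.B.9) go to the DMC and count towards the enrollment-suspension thresholds with no relatedness test.
- *That events under sham cannot be related.* The trial is double-blind, so investigators can choose 'possibly attributed' in either arm.
- *That treatment changes are barred.* Section V.A, item 8 asks for willingness to remain stable. Section X.B.8 provides for stopping study treatment if a major change in medication or treatment is needed in the circumstances it describes.

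Finally, the AE/SAE form (item 37 in Table 2) is not among the pages at hand, so a free-text or 'other' field cannot be ruled out. Such a field would not repair the definition.

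**Conclusion.** The point holds as an internal contradiction with a limited consequence. Section VI.H.1 quotes a standard that includes trial participation, derives from it a rule that does not, and supplies levels that cannot express it. The SAE list in VI.H.2 has the same gap. An event caused by a trial-required medication condition can be classed as unrelated and so miss the relatedness condition in VI.H.3.

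The protocol gives no number of patients on the listed drugs and no expected event rate, so the size cannot be computed. It is probably small. What is at risk is the related label and the reports that depend on it, not the capture of serious events. The conclusion rests on the protocol text alone and assumes that the sponsor applies the definition in VI.H.1 as written. If it applies the full SOP wording when it decides, the practical effect is smaller still, but the text should say so.

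**What to change.** Reconcile VI.H.1 with VI.H.2:

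- Add a separate attribution to the AE levels and to the SAE cause list: participation in the trial or study procedures, including required medication changes.
- Amend the definition of related in VI.H.1 so that it covers both limbs of the standard it quotes.
- State that the new attribution counts as related for the test in VI.H.3, and that it is tabulated apart from device or treatment attribution so that device-related rates are not inflated.

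The cost is one added field on the AE and SAE records and a short change to the text of VI.H. A few more events may be classed as related. No eligibility criterion, medication requirement or other clinical rule changes.

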Acute Treatment Phase. After randomization, and on the first day of each block of treatment, the administrator will determine the motor threshold (MT). The administrator will then deliver left prefrontal active rTMS treatment or Sham (Control) rTMS treatment for 20 to 30 sessions in blocks of 5 sessions. Patients are first tested for “remission” after the first 20 sessions of treatment and then again at the 25th and 30th sessions. “Remission” is defined as a decrease in Hamilton Rating Scale for Depression to 10 or less. **Patients will be retested for remission following the last treatment in each 5-session block.**

- If a participant remits after the first 20 sessions, the participant will enter the 24 week follow-up phase; all participants will receive a minimum of 20 treatments before being evaluated for remission;
- If a participant does not remit after the first 20 sessions of treatment, the participant will be offered an additional 5 or 10 sessions of treatment and retested for “remission” after 25 or 30 sessions. This procedure may continue for a maximum of 30 sessions total treatment.
- If the participant remits, he/she will enter the 24 week follow-up phase during which they will receive a “taper” of treatments over three weeks. The taper will include 3 treatment sessions in the first week, 2 in the second week and 1 in the last week of the taper;
- If a participant does not remit at the end of 30 sessions of treatment or drops out during treatment, the participant will be considered a treatment “failure” for the purpose of the primary analyses. The participant will enter the 24 week follow-up phase. Patients who are treatment “failures” will not receive a “taper” of treatments.

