5. Role of the Site Investigator in Adverse Event Monitoring

The site investigator (as well as other site personnel) will be responsible for following adverse event and adverse device effects reporting requirements. These responsibilities include:

- a. Reviewing the accuracy and completeness of all adverse events/device reports;
- b. Knowing and complying with the VA CIRB (accessible at <http://www.research.va.gov/vacentralirb/>) and VHA Handbook 1058.01 Research Reporting Compliance Requirements section 6 (accessible at http://www1.va.gov/vhapublications/ViewPublication.asp?pub_ID=3116) reporting requirements for unanticipated problems. The VA Central IRB has reporting requirements separate from and beyond Sponsor reporting requirements. See the link above for the Table of Reporting Requirements in Section VI.H.2;
- c. Reporting to the VA Central IRB safety issues reported to the site by the sponsor;

- d. Closely monitoring research participants at each study assessment visit for any new Adverse Events (AEs), Adverse Device Effects (ADEs), Serious Adverse Events (SAEs) which includes Unanticipated Adverse Device Effect (UADE).
- 6. The Study Sponsor (Perry Point CSPCC, CSPCRPCC, and Study Chair) is responsible for the following procedures:
 - a. The Study Pharmacist promptly reviews newly submitted SAE reports to assess completeness of documentation and to determine whether the SAE requires expedited reporting to FDA. SAE reports which may require further reporting to FDA are brought to the attention of the Chair's Office for further medical advice.
 - b. The Perry Point CSPCC tracks receipt of follow-up reports of unresolved SAEs.
 - c. SAE reports that warrant immediate notification to VA Central Office are handled CSPCRPCC forwarded through the Directors of the Perry Point CSPCC and CSPCRPCC to VA Central Office.
 - d. The CSPCRPCC is sent electronic files of adverse events reported semiannually and serious adverse events reported quarterly for assignment of MedDRA codes.
 - e. Tracking of unresolved SAEs by the Sponsor ceases 30 days after the patient completes the study or withdraws consent to be followed.

I. Dropouts and Follow-up Procedures

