If after 100 patients are enrolled 3% of the total enrolled participants have a completed suicide or 6% have attempted suicide, enrollment will be suspended pending an analysis of the SAE data by the DMC. The DMC will review all reports of suicides and suicide attempts carefully to determine whether suicide risks are excessive. If so, recommendations for restart of study enrollment may entail modifications to procedures which would be subject to IRB and FDA approval. If risk of suicide is not deemed excessive, the study will be restarted without modifications. All suicide attempts and completions will be considered SAEs, and as such, will be reported to the study executive committee, Central IRB, and the DMC by the Clinical Research Pharmacist and Study Biostatistician. The DMC will monitor all SAEs regularly (at least every 6 months) throughout the study and assess potential for increased risks to patients. The DMC may also impose requirements for more frequent monitoring of SAEs. We recognize that study termination or modification based on serious adverse events, such as suicide attempts, ultimately rests with the DMC, the Central IRB, and the study

executive committee and that more stringent stopping points may be initiated during the study.

9. Special Procedures for the Monitoring of Seizures

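### The end rules for unresolved SAEs conflict, and after full study exit new suicides and attempts reach the suicide trigger only if someone reports them

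*Protocol*

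**What the plan says.** **Unresolved SAEs.** Protocol VI.H.3 states that if an SAE is open when reported, "the site must monitor and provide SAE follow-up information at least every 30 days until the SAE becomes resolved". No time limit is attached. VI.H.2 deals with a patient who ends participation early: "unresolved SAEs will be monitored and" reported for 30 days after that patient's End of Study date. VI.H.6 item e states: "Tracking of unresolved SAEs by the Sponsor ceases 30 days after the patient completes the study or withdraws consent to be followed".

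**New SAEs.** VI.H.2 states: "Collecting and recording SAEs/UADEs will begin at the time the patient signs the informed consent form and will continue throughout the follow-up phase". It adds that "the investigator must collect all SAEs reported to them for a period of 30 days after the" study's completion, without saying whether that is the patient's completion or the trial's. VI.H.5 item d places active detection at visits: "Closely monitoring research participants at each study assessment visit for any new Adverse Events", with SAEs in the same list.

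**Leaving.** Under VI.E, a participant who drops out during treatment still enters the 24-week follow-up phase. Under VI.J the site investigator may terminate a patient from the study. Under X.B.7 a visibly intoxicated participant is excluded from further participation. VI.I requires attempts to contact a leaver for a Termination Form. VI.J has the primary VA psychiatrist told when a patient is lost.

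**Trigger.** X.B.8 suspends enrolment pending Data Monitoring Committee (DMC) review if, after 100 patients are enrolled, "3% of the total enrolled participants have a completed suicide or 6% have attempted suicide". It classes all suicides and attempts as SAEs.

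**The concern.** There are two linked problems. A site holding an open SAE on day 31 after a patient's early exit is told by one section to continue and by another that the period is over.

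The trigger, meanwhile, has a denominator of everyone enrolled, while its numerator depends on observation that changes when a patient leaves. Before exit, events are sought at visits. After full exit, they arrive only if someone tells the investigator. A rate built this way can understate the true rate, and this rate decides whether enrolment pauses.

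Full exit may also be related to risk. X.B.7 itself links active substance abuse to completed suicide, and it is the section that excludes intoxicated participants. X.B.9 says that patients withdrawn from treatment after a seizure are still followed for protocol assessments; VI.J termination and X.B.7 exclusion carry no such statement.

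**Working it through.** **1. End rules side by side, for an SAE open at exit**

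| Section | Who acts | Stops when |
|---|---|---|
| VI.H.3 | Site | SAE resolves; no limit |
| VI.H.2 | Not named; early leavers | 30 days after the patient's End of Study date |
| VI.H.6 item e | Sponsor | 30 days after completion or withdrawal of consent to be followed |

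From day 31 after exit, VI.H.3 and VI.H.2 give different answers for an early leaver. A site that continues under VI.H.3 may be reporting to a sponsor that has stopped tracking. VI.H.6 item e also names no stop for a patient who is terminated or lost without withdrawing consent. This step needs no assumption.

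**2. Capture of a new suicide or attempt**

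| When it occurs | Route into the data |
|---|---|
| Before exit | Active, at visits |
| After stopping treatment only | Active: the patient is in the 24-week follow-up, with SAE collection and the C-SSRS scheduled |
| After full exit (terminated, excluded, withdrawn, lost) | Passive: only if reported to the investigator, within the VI.H.2 window |

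The gap is confined to the last row. Its length depends on the undefined completion. If completion is the trial's, a reported event is in the window until 30 days after the trial ends. If it is the patient's, the window may close 30 days after that patient is done.

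**3. Trigger counts.** The protocol gives no derivation of the 3% and 6% limits, so there is no figure to reproduce. The count needed is r = the limit × N, rounded up.

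- N = 100: 0.03 × 100 = 3 suicides; 0.06 × 100 = 6 attempts.
- N = 360 (planned total, VIII.A): 10.8, so 11 suicides; 21.6, so 22 attempts.

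I take enrolled to mean randomised, although VI.A.3 also uses the word for the 720 to 800 consented. The counts at N = 100 are the same either way.

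**4. Effect of missed events (illustration).** Let p be the true proportion with an attempt and m the share of those missed. The observed count is Binomial(N, p(1 − m)), and the chance of reaching the trigger is P(X ≥ r). The protocol supplies neither p nor m. I assume p = 8% and m from 0 to 30%, and look once at each N.

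| m | p(1 − m) | P(≥ 6 of 100) | P(≥ 22 of 360) | True rate that shows as 6%: 0.06/(1 − m) |
|---|---|---|---|---|
| 0 | 8.00% | 82.0% | 92.7% | 6.0% |
| 5% | 7.60% | 78.0% | 88.1% | 6.3% |
| 12% | 7.04% | 71.4% | 78.3% | 6.8% |
| 20% | 6.40% | 62.3% | 61.9% | 7.5% |
| 30% | 5.60% | 49.1% | 36.8% | 8.6% |

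For suicides, the true rate that shows as 3% is 0.03/(1 − m): 3.2%, 3.4%, 3.75% and 4.3% for m = 5%, 12%, 20% and 30%.

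**The case against.** **The end rules can be read together.** VI.H.2 is the specific rule for early leavers and could be taken to cap the general duty in VI.H.3; VI.H.6 concerns the sponsor and also uses 30 days. That is a sensible reading, but VI.H.3 contains neither the cap nor a cross-reference, so a site has to guess. The point stands as a reconciliation.

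**A reader might infer that no new events are collected after exit, or that they never reach the trigger.** The text does not support this. VI.H.2 covers all SAEs reported to the investigator, not only unresolved ones, and VI.H.3 requires them to be forwarded within 72 hours of awareness. Events before exit count in full.

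**A reader might infer that the patients at highest risk are the ones lost, from the rules in X.B.8 on safety plans, mania and imminent suicidality.** Those rules mostly stop study treatment, and VI.E puts patients who stop treatment into follow-up. X.B.8 also favours continuing treatment after an attempt if the patient agrees. Only full exits, as in VI.J and X.B.7, open the gap.

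**A reader might put a size on the loss from the 88% retention quoted in I.E.** That figure is another trial's completion of its initial phase. Here such drop-outs are meant to be followed, so 12% is not a full-exit rate.

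**There are other safeguards.** The DMC reviews all SAEs at least every six months and may tighten the stopping points. VI.H.5 refers to IRB and VHA reporting rules that are not reproduced in the protocol. VI.G.16 expects no detectable difference between arms in attempts, so I claim no damage to that comparison. These limit the consequence, but the DMC can review only events that were captured.

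**Conclusion.** The concern holds in a limited form. The conflict between VI.H.2, VI.H.3 and VI.H.6 item e is a matter of text and rests on no assumption. So does the finding that ascertainment after full exit is passive while the X.B.8 denominator keeps those patients.

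The under-count itself is possible rather than shown, and its size is unknown. The illustration depends on an assumed 8% attempt rate, an assumed missed share and a single look. Within those limits, the chance of reaching 6 of 100 falls by about 11 percentage points (82.0% − 71.4% = 10.6) if 12% of attempts are missed, and by about 20 (82.0% − 62.3% = 19.7) if 20% are. The trigger is weakened, not disabled. The primary remission analysis is not affected.

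**What to change.** - Reconcile VI.H.2, VI.H.3 and VI.H.6 item e to one end point for unresolved SAEs, covering patients who complete, withdraw, are terminated or are lost.
- State in VI.H.2 whether the study's completion is the patient's or the trial's.
- State in VI.H.2 that deaths, suicides and suicide attempts are ascertained for every randomised participant to the planned week-24 date, by review of the VA electronic record (CPRS) and contact with the primary VA psychiatrist, unless the patient withdraws consent for record review. Define that date for someone who leaves during acute treatment: with 4 to 11 weeks of treatment (VI.D), it falls 4 + 24 = 28 to 11 + 24 = 35 weeks after treatment starts.
- State in X.B.8 that these events count in the trigger's numerator, and say what enrolled means there.

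**Cost.** An amendment, consent wording and one chart review per full leaver. Each 5% of participants who leave fully adds 0.05 × 360 = 18 reviews. Sites already use CPRS and already communicate with the psychiatrist. One limit remains: with a single review at week 24, an event may enter the count months after it occurred.
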